Use of prosthetics	Use or presence of removable oral prosthesis at the time of clinical evaluation. ➤ Information obtained when conducting the clinical evaluation	1. Total upper arch prosthesis 2. Total lower arch prosthesis 3. Total prosthesis both arches 4. Removable partial upper arch prosthesis 5. Removable lower arch partial denture 6. Removable partial denture both arches

Number of teeth present	Number of teeth present in the mouth at the time of the clinical examination ➤ Information obtained when conducting the clinical evaluation	
 1. 1 to 8 teeth 2. 9 to 16 teeth 3. 17 to 24 teeth 4. 25 to 32 teeth
DTM Treatment	Type of therapy that the patient receives for 6 weeks for the treatment of DTM.	
 1. Transcutaneous electrostimulation therapy and occlusal splint 2. Percutaneous electrostimulation therapy and occlusal splint 3. Occlusal splint

Variables of signs and symptoms of DTM		
Variable	Definición operacional	Escala de medición
Muscle pain	Amount of muscular pain reported by the patient when applying a pressure of 1.5 Kg / cm ² in masseter muscles and 2.4 Kg / cm ² in temporal muscles using a circular tip of a Baseline brand pressure algometer. (52) ➤ Information obtained with visual analog scale when conducting the clinical evaluation.	0 to 10 Where 0 represents the absence of perceived pain, and 10 the maximum amount of pain
Joint pain	Amount of joint pain reported by the patient when applying a pressure of 1.5 Kg / cm ² to the surface area of the ATM using a circular tip of a baseline pressure algometer. (52) ➤ Information obtained with visual analog scale when conducting the clinical evaluation.	0 to 10 Where 0 represents the absence of perceived pain, and 10 the maximum amount of pain
Limitation of mouth opening	Amount of millimeters measured from the incisal edge of the upper anterior teeth to the incisal edge of the lower anterior teeth with a TeraBite ruler. ➤ Information obtained when conducting the clinical evaluation	Millimeters (mm) 
 1. Normal opening (> 40mm) 2. Opening limitation (<40mm.)
Presence of joint noises	Sound detected and recorded by the operator using a stethoscope placed in the anterior atrial area above the TMJ when making mandibular opening and closing movements. ➤ Information obtained when conducting the clinical evaluation	
 1) Not 2) Yes

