The treatment for TMD will be carried out by means of the conventional treatment with an occlusal splint and as an auxiliary method, transcutaneous and percutaneous electrostimulation therapies will be applied by the same operator during the period from August 2020 to June 2021. The appointments for clinical control for signs and symptoms of TMD, splint adjustment, electromyographic records and application of electrostimulation therapy as an adjunct to the use of splint, will be scheduled once a week in the Physiology Laboratory from 9:00 am to 1:00 pm and from 2:00 pm to 6:00 pm: 00pm for six consecutive weeks.

• **Electromyographic recording technique**

The registration system (hardware and software) that will be used for the electromyographic evaluation is the Electromyograph 1.2 UNAM-CINVESTAV, which consists of a two-channel system for the analysis of the electromyographic signal that offers greater precision and facilitates muscle assessment through the estimation made by the software of the RMS for its acronym in English (Root Mean Square) and Hurts Index. (53)

The RMS and Hurts Index will be recorded using three electrodes: one placed at the muscular origin, another at the insertion, and finally one in the behind-the-ear area as a ground or neutral electrode. The RMS recording is performed at maximum intercuspation for 30 seconds; the action potential that is expressed in electrical energy will be recorded in microvolts per second ($\mu\text{V} / \text{s}$).

6 electromyographic recordings will be performed on each patient (one record each week) during the time of splint use. Electromyographic recordings will be scheduled as well as follow-up control appointments, to make adjustments to the physiological occlusal splint.

Occlusal splint fabrication technique

The occlusal splints for the treatment of TMD will be the same for all the participants, they will be made by the Principal Investigator in the Physiology Laboratory of DEPeI, UNAM. The indications for the use of a splint and hygiene will be the same in all patients (the splint is worn 24 hours a day, it is

removed for eating and brushing teeth). The splint is washed with neutral liquid hand soap, no brushing or scrubbing).

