The patient will be positioned on the dental chair, the superficial area of the skin of the masseter muscle will be cleaned with alcohol and cotton. Two Kendall® MediTrace 100 electrodes will be placed in each masseter muscle (right and left), considering the same references that were used for the electrodes placed for the electromyographic recording; the first electrode is placed at the origin of the masseter muscle or superficial area of the mandibular condyle and the second at the insertion of the masseter muscle at the angle of the mandible. After placing the electrodes, the KWD-808 electroacupuncture device will be connected to the patient by means of two double alligator cables; the alligators will be pressed to the metal head of each electrode: the positive pole (red color) will be connected at the origin of the masseter muscle and the negative pole (black color) at the insertion of the masseter muscle.

Before nerve stimulation, all patients will be informed of the perceived sensation, which in some patients will range from imperceptible to barely noticeable or not very noticeable.

The parameters to be used will be: pulse duration until sensory activation and high intensities, but with an established limit to prevent muscle contraction and that allows maximum comfort for 20 minutes. Current will be transmitted with square or rectangular waveform, the stimulation frequency: two frequency bands (low: 210Hz and high 10140Hz.); wave amplitude: 3050 volts, pulse duration: 40100 msec; and the output intensity: 0.70 (for 100Hz). The treatment time will be 20 minutes; the equipment has the quality of timing itself and after time it will stop transmitting a signal to the patient. The treatment will consist of the application of six consecutive therapies programs weekly.

Percutaneous electrical stimulation technique

The transcutaneous electrostimulation therapies will be carried out by the Principal Investigator, who will be trained in the ISSSTE Clinic Specialties East Leonardo Bravo Complex in the acupuncture service under the supervision of [name] [name]. (Surgeon, Specialist in Family Medicine. Training in acupuncture in different institutions. Master's in Medical Education, Doctorate in Education, Professor of various courses in acupuncture from a medical perspective. Academic of the Faculty of Medicine of UNAM.)

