The parameters to be used will be: pulse duration until sensory activation and high intensities, but with an established limit to prevent muscle contraction and that allows maximum comfort for 20 minutes. Current will be transmitted with square or rectangular waveform, the stimulation frequency: two frequency bands (low: 210Hz and high 10140Hz.); wave amplitude: 3050 volts, pulse duration: 40100 msec; and the output intensity: 0.70 (for 100Hz). The treatment time will be 20 minutes: The equipment has the quality of timing itself and after time it will stop transmitting a signal to the patient.

The treatment will be carried out every week with a total of six continuous therapies or if the patient deserves it until the remission of symptoms.

Pilot test

A pilot test of transcutaneous and percutaneous electrical stimulation therapies will be carried out in a selection of 8 patients who wish to participate in the study at the DEPeI Physiology Laboratory. The appropriate placement of the points to be stimulated during therapy, the patient preparation time for therapy, the clinical examination to collect the independent variables, and the electromyographic recording method will be identified.

The electromyography will identify the RMS and Hurts Index values of each recording and the changes in the electrical activity of the masseter muscles will be evaluated during electrostimulation and splint appointments. The criteria for the electromyographic recording method and its duration (30 seconds, measured in microvolts (μV)) will be evaluated.

Processing record methods

The registration of data processing will be carried out in two stages:

- During the first stage, the information obtained with respect to the variables of interest will be recorded in the Clinical History of the Physiology Laboratory of each patient, which will be filled out during the clinical evaluation, electrostimulation therapies and electromyographic record in maximum intercuspation.
- In the second stage, the database will be created, transferring the data recorded in the Information Collection Instruments format for each patient to an Excel spreadsheet, to later perform the statistical analysis in the statistical software Stata version 14.

Statistical data analysis plan

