o A descriptive analysis of the main clinical characteristics of the population studied will be carried out in the case of continuous variables, the mean and standard deviation or the median and its interquartile range will be reported according to its distribution normal and antagonistic as n and percentage (%).

o The muscle effect of electrostimulation therapies within and between groups over time (before and during the 6 weeks of treatment), will be calculated using two-way ANOVA for repeated measures. Furthermore, the significant effect size of the comparison is calculated according to Cohen's effects (small (0.20), moderate (0.50) and large (0.80)).

o To identify the changes in the electromyographic activity of the multifractal analysis (Hurts Index and RMS) recorded by time of the right and left masseter muscles of all subjects, since each subject will be evaluated in 6 instances weekly, multilevel models will be adjusted (56) to describe the effect of the passage of time (T0 = Baseline, T1 = 7 days, T2 = 14 days, T3 = 21 days, T4 = 28 days, T5 = 35 days,

T6 = 42 days) of splint use and electrostimulation therapy and the effect of different explanatory variables on this change as on the initial value.

o All statistical calculations will be carried out in Stata 14 software (StataCorp., 2015).

Organization

a) Human resources

Tutor: [name] [name]

Tutorial Committee: Dra. [name] and [name] [name]

Operator: Mtra. [name]

External advisors: [name] and [name] [name]

b) Material resources:

EQUIPOS	INSTRUMENTAL	MATERIAL	STATIONERY
(1) Unidad odontológica	(10) Diagnostic equipment (mirror, caliper, scanner)	(50) (25 packs) Kendall® Electrodes	(50) Medical record formats -
(1) Electroestimulador de presión "Baseline" (1)	(3) Therbite	(50) (10 packs) Acupoint® needles	Laboratory of Physiology
Electromiógrafo digital CINVESTAV-UNAM	(2) Algometer	0.025mm x 25mm	(50) Informed consent forms
(1) Electroestimulador KWD-808	(100) Slay Tongues	(65) (2 boxes) Manhole covers	(50) Data collection sheets
(1) Computadora		(4 boxes) Gloves (5) Aerosol disinfectant	
(1) Impresora		(3 packs) Gauze	
(1) Cámara fotográfica		(1) Alcohol	
		(2 packs) Cotton	

c) Research development stages:

I. Training stage:

During the first, a review of the literature will be carried out and the methods of applying the therapies will be described.

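### Only the percutaneous arm may depart from six weekly sessions, at an undefined, symptom-based discretion that conflicts with the six-week course set for every group

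*Protocol*

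**What the plan says.** The session rule appears in several places in the Protocol.

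- **GA (Transcutaneous electrical stimulation technique):** "The treatment will consist of the application of six consecutive therapies programs weekly". No exception is given.
- **GB (Percutaneous electrical stimulation technique):** weekly treatment with a total of "six continuous therapies or if the patient deserves it until the remission of symptoms". No other arm has such a clause.
- **All groups (Variables, DTM Treatment):** treatment is defined as "Type of therapy that the patient receives for 6 weeks for the treatment of DTM".
- **All groups (Information gathering methods):** "splint adjustment, electromyographic records and application of electrostimulation therapy as an adjunct to the use of splint, will be scheduled once a week", and this runs "for six consecutive weeks".
- **Analysis (Statistical data analysis plan):** the muscle effect is assessed "within and between groups over time (before and during the 6 weeks of treatment", and the multilevel models describe change up to "T6 = 42 days) of splint use and electrostimulation therapy".

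The device, the electrical settings and the 20-minute session length are worded alike for GA and GB. The session rule is where the two descriptions part. Ha1 predicts a greater fall in RMS and Hurst index in GB than in GA and in the splint-only group.

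**The concern.** GB versus GA is one of the two contrasts in Ha1. To read it as an effect of the route of stimulation, both arms need the same number of sessions or at least the same rule for setting it. The Theoretical framework itself says that results depend on the duration of the stimulus, and that studies differ in how many therapies they give and how often.

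As written, GA's session count is fixed, while GB's may follow the patient's symptoms and the operator's judgement. The same operator gives both therapies and, in placing needles or surface electrodes, knows the allocation. No criterion limits the departure. This defines the intervention, so it belongs in the protocol and is not a detail to leave to a statistical analysis plan.

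**Working it through.** The plan gives no figure to reproduce. The check compares the rules and then asks what each reading of the GB clause does inside the analysed window.

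**Inputs.** Sessions are weekly and last 20 minutes, and the standard course is six (technique sections). Time points run from T0 on day 0 to T6 on day 42 (Specific objectives; Statistical data analysis plan). The standard dose is 6 × 20 = 120 minutes. The day of the first session is not stated, so both possible starts are tried.

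**Step 1: the rules side by side.** GA: six. GB: six, or a number that depends on symptoms. General schedule and treatment definition: six weeks for everyone. The GB clause therefore conflicts with the GA rule and with the protocol's own general rule.

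**Step 2: extension reading.** A GB patient with persisting symptoms continues weekly beyond session six.

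- First session on day 0: sessions one to six fall on days 0, 7, 14, 21, 28 and 35, and a seventh on day 42. T0 is the baseline, so on day 0 the record must precede therapy. With the same order on day 42, the seventh session follows the T6 record.
- First session on day 7: sessions one to six fall on days 7 to 42, and a seventh on day 49, after T6.

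In either case the extra session comes after the last record, and GB and GA have had the same number of sessions at every record.

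**Step 3: stop-at-remission reading.** A GB patient whose symptoms remit after session *k* (*k* = 1 to 5) stops there. Minutes received = 20*k*; shortfall = (6 − *k*)/6.

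| Sessions received | Minutes | Shortfall against 120 |
|---|---|---|
| 1 | 20 | 83% |
| 2 | 40 | 67% |
| 3 | 60 | 50% |
| 4 | 80 | 33% |
| 5 | 100 | 17% |

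These sessions would be lost inside T0-T6, while a GA patient in the same state would go on to six. The figures are per patient. The Protocol gives no remission rate, so no arm-level average can be derived.

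**A side point on the records.** The text speaks of six recordings, but the labels T0 to T6 make seven. The argument in Step 2 needs only that no record is later than day 42.

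**The case against.** The strongest reply is that the clause hardly touches the trial. Six is stated first as the total for GB. The general schedule and the treatment definition make six weeks common to all groups. Asking whether a patient deserves it fits giving more treatment better than withholding it. The English is visibly translated, so the sentence may be a slip or a provision for care after the trial course. On that reading the data up to T6 are essentially unchanged, and the reading that does harm is the less natural one.

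Most of this stands, and it limits the weight of the point. It does not remove the inconsistency. The text does not settle which reading is meant, and an operator who follows the GB section literally may depart from six in that arm alone.

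A reader might infer that GB patients can reach T6 with seven sessions against six in GA. That needs a first session on day 0 with the record before therapy, and then the reverse order on day 42. Information gathering methods fixes no order within a visit, but it lists records before therapy and nothing suggests a switch. The Protocol does not support that inference.

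A reader might also want session counting added as new data collection. Processing record methods already has the clinical history filled out during the electrostimulation therapies, so the count should be obtainable from there.

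**Conclusion.** The inconsistency is real: one stimulation arm has an open, symptom-dependent exception with no criterion or limits, against a fixed six in the other arm and six weeks for every group. Its consequence depends on the meaning.

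- **Extension:** no material effect on the T0-T6 comparison, assuming sessions stay weekly and records precede therapy on the day.
- **Stopping at remission:** between 17% and 83% less stimulation for a GB patient who stops, inside the analysed window. GB versus GA would then compare route and dosing rule together.

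A reader might go further and conclude that the clause builds a dose advantage into GB and favours Ha1. The Protocol does not support this. The extension reading adds nothing before the last record, the stop reading lowers GB's dose, and neither the share of patients affected nor the direction of any bias can be worked out. No actual dose imbalance is shown. This is a minor-to-moderate consistency correction.

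**What to change.** Replace the GB sentence with the rule used for GA, worded identically for both stimulation arms: six weekly sessions, neither stopped because symptoms have remitted nor extended before the T6 record. If continued care is wanted, allow it only after the T6 record, under one written criterion for GA and GB, and keep it outside the T0-T6 comparison. Report the number of sessions each patient received, taken from the existing clinical history.

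The cost is one amended sentence and one tabulated count, with no extra visits, staff or patients. The downside is that a GB patient who still has symptoms waits until after the T6 record for any further session, which could be later on day 42.

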To compare the neuromuscular electrical activity (RMS) and muscle fatigue (Hurst index) of the masseter muscles in three groups of patients with different treatments for TMD (GA = Transcutaneous electrostimulation and splint, GB = Percutaneous electrostimulation and splint, and GC = Occlusal splint.) through 6 electromyographic records scheduled weekly in patients from the Physiology Laboratory of the Division of Graduate Studies and Research (DEPeI) UNAM, admitted during the period from August to December 2020.

Specific objectives

- o Register the sociodemographic and clinical variables (age, sex, TMD, BMI, systemic diseases, use of prostheses, number of teeth present, drug intake) prior to TMD treatment in patients admitted to the DEPeI UNAM Physiology Laboratory during the period from August to December 2020.
- o Record the neuromuscular electrical activity (RMS) and muscle fatigue (Hurst Index) of the masseter muscles of the three groups of patients with different treatments for TMD (GA = Transcutaneous electrostimulation and splint, GB = Percutaneous electrostimulation and splint, and GC = Occlusal

splint) by means of 6 electromyographic recordings scheduled weekly (T0 = Basal, T1 = 7 days, T2 = 14 days, T3 = 21 days, T4 = 28 days, T5 = 35 days, T6 = 42 days) in patients from the Laboratory Physiology of the DEPeI, UNAM, admitted during the period from August to December 2020.

o Record TMD signs and symptoms (muscle pain, joint pain, mouth opening limitation, presence of joint sounds and heart rate) during TMD treatments through 6 weekly scheduled evaluations (T0 = Baseline, T1 = 7 days, T2 = 14 days, T3 = 21 days, T4 = 28 days, T5 = 35 days, T6 = 42 days) in patients from the Physiology Laboratory of DEPeI, UNAM, admitted during the period from August to December 2020.

o Identify the changes in neuromuscular electrical activity (RMS) and muscle fatigue (Hurst Index) of the masseter muscles in each group (GA = Transcutaneous electrostimulation and splint, GB = percutaneous electrostimulation and splint, and CG = Occlusal splint) during the TMD treatment (T0 = Baseline, T1 = 7 days, T2 = 14 days, T3 = 21 days, T4 = 28 days, T5 = 35 days, T6 = 42 days) in patients from the Physiology Laboratory of DEPeI, UNAM, admitted during the period from August to December 2020.

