percutaneous electrostimulation and splint, and GC = Occlusal splint) during treatment of TMD according to the sociodemographic and clinical variables (age, sex, TMD, BMI, systemic diseases, use of prostheses, number of teeth present, drug intake), in patients of the Physiology Laboratory of DEPeI, UNAM, admitted during the period from August to December 2020.

Hypothesis

Ha1: There will be a greater decrease in neuromuscular electrical activity (RMS) and muscle fatigue (Hurst index) of the masseter muscles in the treatment group with percutaneous electrostimulation (GB = percutaneous electrostimulation and splint) compared to the values of the electrostimulation groups transcutaneous (GA = transcutaneous electrostimulation and splint) and the control group (CG = Occlusal splint) of patients from the Physiology Laboratory of the Division of Postgraduate Studies and Research (DEPeI), UNAM, admitted during the period from August to December 2020 .

Ho1: There will be no decrease in neuromuscular electrical activity (RMS) and muscle fatigue (Hurst index) of the masseter muscles in the treatment group with percutaneous electrostimulation (GB = percutaneous electrostimulation and splint) compared to the values of the electrostimulation groups transcutaneous (GA = transcutaneous electrostimulation and splint) and the control group (CG = Occlusal splint) of patients from the Physiology Laboratory of the Division of Graduate Studies and Research (DEPeI) UNAM, admitted during the period from August to December 2020.

Material and methods

Type of study

Randomized clinical trial

Study population

Patients with TMD who will enter the Physiology Laboratory of the Division of Graduate Studies and Research (DEPeI) UNAM, during the period from August to December 2020.

The DEPeI UNAM Physiology Laboratory attends approximately 900 patients per year, of which 168 first-time patients are referred from other specialty clinics at DEPeI UNAM. Around 100 appointments are scheduled per month, most of them are for treatment controls through occlusal splint adjustment and electromyographic records. The patients received by the Physiology Laboratory are referred by the Reception and Diagnosis Clinic (Postgraduate), the specialty clinics of the DEPeI, stomatological services of hospitals and private clinics, among others.

Selection and sample size

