The selection of the sample will be carried out by a convenience sampling which will be carried out based on the clinical evaluation (considering the inclusion and exclusion criteria) in patients with a diagnosis of TMD who will enter the DEPeI Physiology Laboratory during the period from August 2020 to December 2020.

The selected sample will be divided into three groups (GA = transcutaneous electrostimulation and splint, GB = percutaneous electrostimulation and splint, GC = splint); the allocation by group will be made by means of a randomization in balanced blocks. For this process, a series of blocks will be assembled made up of a certain number of cells in which the types of treatment are included. The number of blocks will be determined by the number of participants to be included in the study and the number of cells that it has been decided to include in each block. Each block will contain in each cell one of the treatment alternatives and within each block there must be a balanced number of possible treatments.

The recruitment period will be carried out during the period from August to December 2020, patients with a diagnosis of temporomandibular dysfunction (TMD) will be recruited who will enter the Physiology Laboratory of the Division of Postgraduate Studies and Research (DEPeI) UNAM, during the period from August to December 2020. The diagnosis of TMD will be carried out by the main researcher (Doctoral Student of the Master's and Doctoral Program in Dental and Health Medical Sciences) using the Diagnostic and Research Criteria for Temporomandibular Disorders (CDI / TTM) . (50) (Annex 1 and 2)

Sample size calculation

The characteristic analysis used to analyze the comparison of means in more than two groups corresponds to the one-way analysis of variance (ANOVA). (51) The sample size was estimated for ANOVA (Sample size For ANOVA).

Since the means are unknown, the background of the research is used: Camargo in 2018 (48), reports the electromyographic changes (RMS) of the trapezius muscles of four study groups with different treatments (G1 = superficial electro acupuncture, G2 = deep stimulation of trigger points, G3 = combination of acupuncture and electro acupuncture and G = 4 control group), before and after treatment.

For the sample size calculation, only the RMS values after the treatment used in groups 1, 2 and 4 were taken.

Electromyographic values (RMS) of the trapezius muscle of the three groups studied.		

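### The between-group test treats baseline (T0) as one more outcome visit and not as a covariate: valid, but it gives up precision the trial could have at no cost

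*Protocol*

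**What the plan says.** The Statistical data analysis plan states that the effect "within and between groups over time (before and during the 6 weeks of treatment), will be calculated using two-way ANOVA for repeated measures". T0 is thus one level of the time factor. The next bullet plans multilevel models for RMS and the Hurst index over T0 to T6, describing the effect of time and "the effect of different explanatory variables on this change as on the initial value". T0 is a modelled value there too. Neither bullet enters T0 as a covariate or gives the arms a common baseline mean, and neither says which ANOVA term tests the hypothesis.

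Ha1 is a between-group claim for percutaneous stimulation (GB) against the other two arms: "There will be a greater decrease in neuromuscular electrical activity (RMS) and muscle fatigue (Hurst index". Allocation is randomised in balanced blocks. The sample size used a third quantity, since "only the RMS values after the treatment used in groups 1, 2 and 4 were taken" in a one-way ANOVA.

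The number of recordings is given in two ways. The Specific objectives list seven times, ending "T5 = 35 days, T6 = 42 days) in patients from the Laboratory Physiology", while the Electromyographic recording technique says "6 electromyographic recordings will be performed on each patient (one record each week".

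**The concern.** Randomised arms have equal expectation at T0, so T0 carries no information about treatment as an outcome. As a covariate it explains part of the between-patient spread in later values. The planned ANOVA offers two terms for the between-group question, and neither uses T0 in that way:

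- The group main effect averages T0 with the treated visits, so the contrast shrinks.
- The group-by-time term tests any difference in profile and handles T0 by subtraction, which is less efficient than regression on T0.

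At stake is the precision of the GB–GA and GB–GC comparisons with about 25 evaluable patients per arm. This concerns a method the protocol states, not a detail left to a later document.

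**Working it through.** **The plan's own figures.** Group means 90.205, 79.99 and 81.27 have grand mean 83.82 and squared deviations summing to 61.94. Then F = (4 × 61.94 / 2) / 74.2155 = 1.669, as tabulated, and Cohen's f = √((61.94/3)/74.2155) = 0.527. The dropout step reproduces: 75.46/0.9 = 83.8, so 84. The 75.46 itself does not follow from f = 0.527 (38 patients at 80% power, 59 at 95%), and no target power is stated. That is a separate matter. Only the 25 evaluable per arm is used here.

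**Degrees of freedom.** Three arms and seven times: (3−1)(7−1) = 12. Six recordings: (3−1)(6−1) = 10.

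**Dilution of the main effect.** An effect constant from T1 shrinks to 6/7 = 0.857 once T0 is averaged in. An effect building linearly to T6 shrinks to (0+1+…+6)/(6×7) = 0.5 of its T6 size.

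**Single-visit variance (unit SD, T0–visit correlation r).** Change: 2(1−r). T0-adjusted: 1−r². Ratio: 2/(1+r) = 1.54, 1.33 and 1.18 at r = 0.3, 0.5 and 0.7.

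**Power, like for like.** Assumptions not in the protocol: GB 0.7 SD lower, GA = GC, unit SD, 25 per arm, α = 0.05 (the alpha in the sizing table). Noncentrality is 8.167 × a²/V. Here 8.167 = 25 × 0.3267 (the sum of squared arm deviations), a is the fraction of the effect the contrast sees, and V is its variance. F has 2 and 72 df, or 71 with a covariate.

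At T6 (a = 1):

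| T0–T6 correlation | unadjusted (V = 1) | change | T0-adjusted |
|---|---|---|---|
| 0.3 | 71% | V = 1.40, 55% | V = 0.91, 75% |
| 0.5 | 71% | V = 1.00, 71% | V = 0.75, 83% |
| 0.7 | 71% | V = 0.60, 91% | V = 0.51, 95% |
| AR(1) 0.7, so 0.7⁶ = 0.118 | 71% | V = 1.765, 45.5% | V = 0.986, 71% |

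Effect constant over T1–T6:

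| Structure | main effect including T0 (a = 6/7) | T1–T6 mean, unadjusted | T1–T6 mean, T0-adjusted |
|---|---|---|---|
| equal correlation 0.5 | V = 0.571, 82% (81% by simulation) | V = 0.583, 92% | V = 0.333, 99% |
| AR(1) 0.7 | V = 0.518, 86% | V = 0.563, 93% | V = 0.445, 97% |

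So roughly half of the gain over the main effect comes from leaving T0 out of the average, and the rest from the covariate.

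**Group-by-time term, 12 df with and without T0 adjustment.** Half the sizing effect (f = 0.26), 75 patients, equal correlation. Constant effect: 0.31, 0.44 and 0.71 unadjusted against 0.75, 0.73 and 0.86 adjusted, at correlations 0.3, 0.5 and 0.7. At correlation 0.5, a linear effect gives 0.40 against 0.51, and a fading one 0.47 against 0.55.

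**At the full sizing effect (f = 0.53).** Constant effect: main effect 0.98 to 1.00, group-by-time 0.94 to 1.00. Linear effect: group-by-time 0.91 to 1.00, main effect 0.90 down to 0.64 as the correlation rises.

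**The case against.** The planned analysis is conventional. Under randomisation it does not bias the group comparison. Group-by-time compares changes, which is how Ha1 is worded, and it subtracts chance imbalance at T0. All of that stands.

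Four stronger readings are tempting and are not supported:

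- A reader might set group-by-time against a T0-adjusted test at T6, in a linear scenario with the 0.7 SD effect, and attribute the whole gap to the handling of T0. Simulated power is 61% against 83% at equal correlation 0.5, and 49% against 71% under AR(1) 0.7. But a T6 test with no adjustment already has 71%. Part of the first gap and nearly all of the second come from choosing the visit at which the effect peaks.
- A reader might infer that T0 in the series serves no purpose. The Specific objectives ask for change within each arm, and that needs T0.
- A reader might infer that the multilevel model estimates a treatment effect on the initial value. The text says explanatory variables, and the matching objectives list age, sex, BMI, teeth and drug intake, for which such an effect is legitimate.
- A reader might infer that every planned analysis loses to adjustment at T6. If the multilevel model fits time linearly, which the protocol does not say, and the effect is linear, a 2-df slope test with free baselines has 76%, 89% and 99% at equal correlations 0.3, 0.5 and 0.7. T0-adjusted T6 has 75%, 83% and 95%. Under AR(1) 0.7 the slope test falls to about 42–46%.

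**Conclusion.** The point holds as one of efficiency. The ANOVA leaves T0 unused as a covariate: its main effect is diluted, and its group-by-time term corrects for T0 by subtraction only. In each matched comparison run, T0 adjustment had power at least as high. The gain ranges from almost nothing over an unadjusted T6 value (AR(1) 0.7) to 12 points at T6 (equal correlation 0.5), and to 11–17 points over the main effect when the effect is constant.

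These sizes rest on an assumed effect, assumed correlations and an assumed course over time, none of which the protocol gives. If the true effect matches the sizing data and is constant, little is lost. Those data have four values per group and p = 0.24, so a smaller effect is plausible, and then the loss matters. The documents do not support calling the planned comparison biased or invalid on this ground. The change should be made, but the trial does not fail without it.

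**What to change.** For the between-group comparison, replace the ANOVA by a model of the post-baseline visits with T0 of the same measure as covariate, plus arm, visit and arm-by-visit. Essentially the same result comes from a multilevel model of T0–T6 with visit as a category and arm means constrained equal at T0. That version also keeps the within-arm change objective in one model.

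Name in advance the single contrast that tests Ha1: the T1–T6 mean or T6. T6 alone is not best for every course. With a constant effect under AR(1) 0.7, T0-adjusted T6 has 71% power against 86% for the planned main effect, while the T0-adjusted T1–T6 mean has 97%. Show T0 by arm descriptively, and state whether there are six or seven recordings.

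The cost is a few sentences in the analysis plan. T0 is already scheduled for every patient, so no new data and no extra patients are needed.
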